6.2. Timing of Analyses

There will be an interim immunogenicity analysis, which may be used to optimize and prioritize research laboratory assays for exploratory outcomes. The interim immunogenicity analysis will include all available antibody data for the first 20 participants who complete Visit 6, which includes data addressing the primary and secondary objectives, as well as several exploratory objectives.

The final analysis will be performed when all enrolled participants have completed the day 181 visit, the clinical database has been cleaned, monitored, and locked, and data is available for all secondary immunogenicity measures. Exploratory immunogenicity assays will be determined and performed pending the results of the interim immunogenicity analysis. The results for primary and secondary endpoints, including safety data, will be reported in the primary Clinical Study Report (CSR). A CSR addendum will be prepared to report the results for exploratory endpoints and any additional results.

6.3. Analysis Populations

Demographic and baseline characteristics will be presented for all enrolled participants. All safety summaries will be presented for the safety population. Immunogenicity measures will be presented for the Immunogenicity and per protocol (PP) populations. A tabular listing of all participants, visits, and observations excluded from analyses will be provided in the CSR.

6.3.1. Immunogenicity Populations

For the primary outcome analysis, the immunogenicity population at a specified follow-up visit will include all eligible participants who have received all doses of study product prior to that visit and have immunogenicity data available for that visit. For this study the Immunogenicity population includes all participants who received at least one dose of study vaccine and contributed at least one sample for immunogenicity testing for which valid results were reported. To account for participants having data available only for a subset of assays, assay-specific populations will be defined. For example, the assays for vaginal mucosal specimens will only include female participants in the immunogenicity population, and rectal mucosal biopsy assays will only include biopsy cohort participants in the immunogenicity population. The population is defined for the participant at baseline, such that even when there is a missing value at a certain follow up visit, the participant will be included in the immunogenicity population.

For analyses using the Immunogenicity population, participants will be classified according to the study product received.

6.3.2. Per Protocol (PP) Populations for Immunogenicity

Per-protocol populations will be defined that further restrict the immunogenicity analysis populations to exclude participants with major protocol deviations or events that may impact study product effectiveness or the ascertainment or interpretation of assay results. The per protocol (PP) population includes all participants in the Immunogenicity subset with the following exclusions: 1) Data from all available visits for participants found to be ineligible at baseline or during follow-up. 2) Data from all visits subsequent to major protocol deviations, such as: a) at least one dose of study vaccination not received; b) at least one dose of study vaccination received at > 4 days out of window.

6.3.3. Safety Population

The safety analysis population includes all participants who received at least one dose of study treatment. For analyses using the safety population, participants will be grouped by study treatment received.

6.4. Covariates and Subgroups

Randomization was stratified by sex; however, the protocol does not define any formal subgroup analyses, and the study is not adequately powered to perform subgroup analyses.

6.5. Missing Data

All attempts will be made to collect all data per protocol. As missing data are expected to be minimal, no imputation will be performed for missing values. Any data point that appears to be erroneous or inexplicable based on clinical judgment will be investigated as a possible outlier. If such data points are identified as scientifically valid outliers, sensitivity analyses will be performed to examine the impact of including or excluding the outliers. Any substantive differences in these analyses will be reported.

If a participant missed visits, discontinued vaccinations or early terminated due to Covid-19, the participant will be recorded and highlighted in the report.

6.6. Interim Analyses and Data Monitoring

There will be an interim immunogenicity analysis, which may be used to optimize and prioritize research laboratory assays for exploratory outcomes. Results of the interim analyses will not be used to make any decisions concerning the conduct of this trial.

The interim immunogenicity analysis will include all available antibody data for the first 20 participants who complete Visit 6, which includes data addressing the primary and secondary objectives, as well as several exploratory objectives. The interim report will be prepared by the unblinded statistician at the SDCC after all relevant immunogenicity data through Visit 6 are received. Results will be shared only with relevant study personnel (i.e. PI, laboratory investigator(s), and DMID) and only in aggregate by treatment arm. Study personnel will remain blinded to individual participant treatment assignments.

The interim immunogenicity analyses will include summaries of descriptive and aggregate antibody data against antigens from *N. gonorrhoeae* and *N. meningitidis* stratified by antigen, specimen type (serum or mucosal), pre- versus post-treatment timepoints, and treatment arm (4CMenB or placebo). No hypothesis tests

or modeling will be included in the interim immunogenicity analysis. This interim analysis of the data is not intended to impact the conduct of this trial. No statistical adjustments are planned.

As defined in the protocol, the SMC will review data at specified times during the course of the study for participant and overall study progress and will conduct ad hoc reviews as appropriate when a halting rule is met or for immediate concerns regarding observations during this study.

6.7. Multiple Comparisons/Multiplicity

There is only one primary endpoint at 5 timepoints. No formal hypothesis test of the primary outcome will be performed. No adjustments for multiple comparison are planned. No adjustment to the alpha level for CIs will be performed.

7. STUDY PARTICIPANTS

7.1. Disposition of Participants

The disposition of participants in the study will be tabulated by Treatment group ([Table 6](#)). The table shows the total number of participants who screened, enrolled, received at least one dose, discontinued dosing or terminated from study follow-up, and those completing the study. The composition of analysis populations, including reasons for participant exclusion, by treatment arm, is presented in [Table 7](#) and [Table 8](#).

Participants excluded from analysis populations will also be summarized in [Listing 5](#). [Table 9](#) shows the dates of first treatment received by group. [Table 10](#) will present a summary of the reasons that participants were screened but not enrolled. A listing of all participants that received study product is provided in [Listing 1](#). A flowchart showing the disposition of study participants, adapted from the Consort Statement will be included ([Figure 1](#)). This figure will present the number of participants screened, enrolled, lost to follow-up, and analyzed, by treatment arm. A listing of participants who discontinued dosing or early terminated from study follow-up and the reason will be included in [Listing 2](#). Participants who terminated early or discontinued vaccinations due to the Covid-19 pandemic will be highlighted in the listing.

7.2. Protocol Deviations

A summary of participant-specific protocol deviations will be presented by the deviation category, deviation type, and Treatment group for all participants ([Table 3](#)). Major deviations will be reviewed for possible participant exclusion from the per protocol population, including deviations affecting eligibility at baseline, product administration deviations, primary endpoint missing data, and deviations relating to prohibited medications. See [Section 6.3.2](#) for per protocol exclusion definitions. All participant-specific protocol deviations and non-participant specific protocol deviations will be included in [Appendix 3](#) as data listings ([Listing 3](#) and [Listing 4](#), respectively). Participants who had a protocol deviation due to the Covid-19 pandemic will be highlighted in the listing.

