8. IMMUNOGENICITY EVALUATION

This study was not designed to test a specific null hypothesis, rather, the objective was to characterize the immune response to GC elicited by the 4CMenB vaccine as compared with the placebo (normal saline) in healthy adult participants. Immunogenicity analysis will be presented for the Immunogenicity and PP populations. Immune responses for the study vaccine (4CMenB or placebo) will be summarized at each time point presented by study arm. Descriptive summary statistics will be provided for all assays and time points. For serum and mucosal antibody (IgG, IgA) assays by ELISA, the GMT and geometric mean fold rise (GMFR) will be calculated for each time point, (Days 1, 29, 43, 57, and 181 for GMT, and Days 29, 43, 57, and 181 for GMFR) in each study arm. Point estimates and their 95% confidence intervals will be reported for each time point. The distribution of titers will also be graphically summarized using reverse cumulative frequency distributions.

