	Deviation with Treatment administration schedule	x	xx	x	xx	x	xx
	Deviation with Follow-up visit schedule	x	xx	x	xx	x	xx
	Deviation with Treatment administration	x	xx	x	xx	x	xx
	Deviation with Protocol procedure/assessment	x	xx	x	xx	x	xx
	Deviation with Blinding policy/procedure	x	xx	x	xx	x	xx
	Other	x	xx	x	xx	x	xx
Per Protocol Immunogenicity Analysis Population-assays with vaginal mucosal specimen	Any protocol deviation	x	xx	x	xx	x	xx
	Deviation with Eligibility/enrollment	x	xx	x	xx	x	xx
	Deviation with Treatment administration schedule	x	xx	x	xx	x	xx
	Deviation with Follow-up visit schedule	x	xx	x	xx	x	xx
	Deviation with Treatment administration	x	xx	x	xx	x	xx
	Deviation with Protocol procedure/assessment	x	xx	x	xx	x	xx
	Deviation with Blinding policy/procedure	x	xx	x	xx	x	xx
	Other	x	xx	x	xx	x	xx
Notes: N = Number of participants enrolled in each group The number of participants may be different at each visit; For each specific assay, the number of participants may be different.							

Table 9: Dates of First Treatment by Treatment Group

Dates of Dosing	4CMenB (N=X)	Placebo (N=X)	All Participants (N=X)
Total (Entire period of enrollment)			
DDMMYYYY-DDMMYYYY [categorize based on length of enrollment period]	x	x	x
Notes: The dates of dosing will be categorized by 3 month period. N = Number of participants enrolled in each group			

Table 10: Ineligibility Summary of Screen Failures

Inclusion/Exclusion Category	Inclusion/Exclusion Criterion	n ^a	% ^b
Inclusion and Exclusion	Number of participants failing any eligibility criterion	x	xx
Inclusion	Any inclusion criterion	x	xx
	[inclusion criterion 1]	x	xx
	[inclusion criterion 2]	x	xx
	[inclusion criterion 3]	x	xx
Exclusion	Any exclusion criterion	x	xx
	[exclusion criterion 1]	x	xx
	[exclusion criterion 2]	x	xx
	[exclusion criterion 3]	x	xx
Eligible but Not Enrolled		x	xx

^a More than one criterion may be marked per participant.

^b Denominator for percentages is the total number of screen failures.

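### SAP 7.2 and 6.3.2, read together, let one missed rectal sample remove valid later results of a correctly dosed participant from the per-protocol analysis

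*SAP*

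**What the plan says.** SAP 7.2 says that "Major deviations will be reviewed for possible participant exclusion from the per protocol population". The types it names are deviations affecting baseline eligibility, "product administration deviations, primary endpoint missing data, and deviations relating to prohibited medications". It sends the reader to 6.3.2 "for per protocol exclusion definitions".

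SAP 6.3.2 gives the purpose of the PP restriction: to leave out deviations or events that could alter how well the product works, or how an assay result is obtained or read. It excludes all data from ineligible participants and, as its second rule, "Data from all visits subsequent to major protocol deviations, such as: a) at least one dose of study vaccination not received". The only other example is a dose more than 4 days out of window.

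The primary endpoint is rectal IgG at Days 1, 29, 43, 57 and 181 (SAP 3.2.1). Serum IgG is secondary at the same visits (SAP 3.2.2).

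SAP 6.3.1 treats a gap differently for the Immunogenicity population: "even when there is a missing value at a certain follow up visit, the participant will be included in the immunogenicity population". SAP 8 states: "Immunogenicity analysis will be presented for the Immunogenicity and PP populations".

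The Table 8 shell tallies reasons for PP exclusion by generic category, among them the follow-up visit schedule and "Deviation with Protocol procedure/assessment". The Table 3 shell shows what those categories hold: a missed visit in the first, an uncollected specimen in the second.

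**The concern.** A PP analysis here should show the antibody response in participants who were eligible and dosed as planned. A missing Day 29 rectal sample says nothing about dosing and does not invalidate a Day 57 rectal or serum ELISA. It therefore falls outside the purpose that 6.3.2 states for PP exclusion.

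If it is nevertheless handled as a major deviation under 6.3.2, the PP set becomes, at each visit, the participants with no earlier missed rectal sample. That selects on completeness of the outcome, not on adherence. Tables 14 and 16 report the Immunogenicity and PP populations in successive blocks, and a reader will take a difference between the blocks as an effect of adherence. With 10 participants planned on placebo, losing even one or two usable results at a visit is noticeable.

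**Working it through.** **A figure to reproduce.** The plan gives no figure for missed samples. Its nearest number is the Ng OMV ratio in Protocol Table 2 at 40/10, 1.23 (0.85 to 1.79). The ln SDs implied by the GMT intervals are ln(49303/42224)/t(0.975, 39) × √40 = 0.485 for vaccine and ln(56156/34297)/t(0.975, 9) × √10 = 0.689 for placebo. A pooled two-sample t interval with these SDs gives 0.845 to 1.793, which agrees. I take the figure no further. It comes from a cited study that Protocol 2.1 describes in terms of serum antibodies, and the protocol says there are no mucosal data. Tables 14 and 16 also report GMT and GMFR within each arm and no between-arm ratio.

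**One participant.** Take someone with both doses in window who misses only the Day 29 rectal sample. If that is handled as a major deviation, visits after Day 29 go:

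| | Day 1 | Day 29 | Day 43 | Day 57 | Day 181 |
|---|---|---|---|---|---|
| Rectal IgG | kept | missed | removable | removable | removable |
| Serum IgG | kept | kept | removable | removable | removable |

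Rectal: 3 of the 4 collected results. Serum: 3 of 5, if the deletion is not confined to the rectal assay. SAP 6.3.2 does not say whether it is.

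**How many participants.** Let p be the chance of a missed rectal sample per visit, the same at each visit and independent across visits. This is an assumption; SAP 6.5 says only that missing data should be minimal. With k earlier rectal visits, the share whose Day 181 data could be deleted is 1 − (1 − p)^k.

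I take k = 3 (Days 29, 43, 57) as the main case. The Table 7 shell lists a missing baseline sample as a reason for exclusion from the Immunogenicity population itself, so on that reading a Day 1 miss affects both populations. With Day 1 misses also counted, k = 4.

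| p | k = 3 | k = 4 |
|---|---|---|
| 2% | 1 − 0.98³ = 5.9% | 1 − 0.98⁴ = 7.8% |
| 5% | 1 − 0.95³ = 14.3% | 1 − 0.95⁴ = 18.5% |
| 10% | 1 − 0.90³ = 27.1% | 1 − 0.90⁴ = 34.4% |

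**Expected Day 181 rectal N**, with k = 3 and all Day 1 samples obtained. Available is n(1 − p); left in the PP set is n(1 − p)⁴.

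| p | 4CMenB (n = 40): available → PP | Placebo (n = 10): available → PP |
|---|---|---|
| 2% | 39.2 → 36.9 | 9.8 → 9.2 |
| 5% | 38.0 → 32.6 | 9.5 → 8.1 |
| 10% | 36.0 → 26.2 | 9.0 → 6.6 |

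Both tables suppose that the review excludes every such case, so at a given p they show the most that the wording allows under the later-visits rule.

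**The case against.** The strongest reply is that the plan does not order any of this. Section 7.2 speaks of possible exclusion after review and defers to 6.3.2. The situations named there are ineligibility, a dose not received and a dose well out of window; missing samples are absent. A reader might infer that the deletion follows automatically, and the documents do not support that. What stands is that the 6.3.2 examples are illustrative, that 7.2 itself counts missing primary-endpoint data as a major deviation, and that neither section gives a criterion for the review. The unit is also unsettled: 7.2 speaks of excluding participants, 6.3.2 of dropping later visits.

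A reader might also infer that serum data are certain to be lost, because Table 8 has an overall PP row. A row label does not establish that. SAP 6.3.1 provides for assay-specific populations, 6.3.2 refers to PP populations in the plural, Table 8 has a separate vaginal block, and its footnotes let N differ by visit and by assay. Serum loss is possible, no more. Likewise, Table 8 counts reasons by category; it is not itself an exclusion rule.

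The reply can add that the effect would be visible. SAP 6.3 promises a listing of excluded participants, visits and observations, and Listing 5 marks where available data were removed and why. This limits the harm, but it does not explain why valid results should be removed.

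Independence across visits is a further weak point. If misses cluster in the same people, fewer participants are affected, and those who are have less later rectal data to lose.

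**Conclusion.** The point holds as a defect of wording with a real possible consequence. The two sections permit removal of valid later rectal results, and perhaps serum results, from a correctly dosed participant because of one missed rectal sample. That does not fit the stated purpose of the PP population, and it can make the PP and Immunogenicity blocks of Tables 14 and 16 differ for reasons unrelated to adherence.

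The reach is limited. Only the PP results are affected, the analyses are descriptive with no formal test of the primary outcome (SAP 6.7), and the Immunogenicity population keeps the data. The loss for a missed Day 29 sample follows from the visit schedule. The percentages are illustrative: they rest on assumed miss rates, independence, and a review that always excludes.

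A reader might go on to infer a calculable bias in the 4CMenB to placebo ratio, or that losses would come mainly from people who decline anoscopy. The documents support neither. They give no reason for missed samples, and willingness to provide rectal secretions is an inclusion criterion (Protocol 5.1.1). The only available SDs are the serum-based ones behind Table 2, and the direction of any difference between those removed and those kept is unknown.

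**What to change.** - In SAP 7.2, delete missing primary-endpoint data from the deviations reviewed for PP exclusion.
- In SAP 6.3.2, state that a missing or invalid specimen removes only that assay at that visit and is not a major deviation for PP purposes.
- In the Table 8 shell, count uncollected specimens and missed follow-up visits (the Table 3 subtypes) as visit- and assay-specific exclusions.
- Keep participant-level or subsequent-visit exclusion for eligibility, dosing and prohibited-medication deviations, and for other events that could affect product effectiveness or assay interpretation. Limiting it to eligibility and dosing alone would drop legitimate PP exclusions.

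The cost is a few sentences of SAP text and one table shell, with no new data. The PP N will vary by visit and assay, which the Table 8 footnotes already allow.

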8. IMMUNOGENICITY EVALUATION

This study was not designed to test a specific null hypothesis, rather, the objective was to characterize the immune response to GC elicited by the 4CMenB vaccine as compared with the placebo (normal saline) in healthy adult participants. Immunogenicity analysis will be presented for the Immunogenicity and PP populations. Immune responses for the study vaccine (4CMenB or placebo) will be summarized at each time point presented by study arm. Descriptive summary statistics will be provided for all assays and time points. For serum and mucosal antibody (IgG, IgA) assays by ELISA, the GMT and geometric mean fold rise (GMFR) will be calculated for each time point, (Days 1, 29, 43, 57, and 181 for GMT, and Days 29, 43, 57, and 181 for GMFR) in each study arm. Point estimates and their 95% confidence intervals will be reported for each time point. The distribution of titers will also be graphically summarized using reverse cumulative frequency distributions.

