10.2 Sample Size Considerations

A total of approximately 50 (maximum of 60), subjects will be enrolled and randomized to one of two study arms based on a 4:1 allocation ratio to the 4CMenB arm and placebo arm, respectively. The 4:1 allocation ratio was not selected based on any formal statistical criteria but instead was selected to maximize the number of subjects administered 4CMenB, and thus maximize the amount of immunogenicity data collected on subjects administered 4CMenB. Of the approximate 50 subjects, approximately 20 subjects will be enrolled into the Rectal Mucosal Biopsy Cohort. As with the overall sample size, this number was not selected based on any statistical criteria but was selected weighing the feasibility of enrolling subjects who would consent to the biopsy procedure against ensuring ample data was collected via rectal mucosal biopsy as there are no data on the impact of 4CMenB on immunologic responses at the human mucosal surfaces where GC is typically encountered.

The study is not designed to formally test any hypotheses associated with the immunogenicity data. Using the ELISA GMT estimates reported in [Table 2](#) of Semchenko et al.,¹³ estimated GMT 95% confidence intervals were calculated for the 4CMenB group using the post-vaccination estimates and for the placebo group using the pre-vaccination estimates. [Table 2](#) provides the estimated GMTs and GMT ratios between groups. To account for a small percentage of the approximate 50 randomized subjects not being eligible for the primary analysis (e.g., due to not having immunogenicity data available), a range of sample sizes from 36 to 50 was explored.

Table 2: 95% Confidence Intervals for GMTs and GMT Ratios across a range of Sample Sizes and Antigens

| N (Vaccine / Placebo) | Antigen ^a | Treatment Group | GMT Estimate | GMT 95% CI | GMT Ratio | GMT Ratio 95% CI |
|-----------------------------|----------------------|--------------------|-----------------|-----------------|--------------|---------------------|
| 30 / 6 | Ng OMV | Vaccine | 42224 | 35234, 50601 | 1.23 | 0.77, 1.97 |
| | | Placebo | 34297 | 16638, 70697 | | |
| | Ng whole cell | Vaccine | 78793 | 61639, 100721 | 1.62 | 0.86, 3.05 |
| | | Placebo | 48503 | 19329, 121713 | | |
| | Nm whole cell | Vaccine | 388023 | 262806, 572900 | 4.00 | 1.53, 10.47 |
| | | Placebo | 97006 | 29287, 321311 | | |
| | Ng rNHBA | Vaccine | 1176267 | 876783, 1578046 | 34.3 | 16.98, 69.26 |
| | | Placebo | 34297 | 16638, 70697 | | |

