10.5.3 Immunogenicity Analysis Plan

For the analyses of the primary and secondary immunogenicity outcomes, the GMT and geometric mean fold rise (GMFR) for ELISA titers will be calculated for Days 1, 29, 43, 57, and 181 in each study arm. Point estimates and their 95% confidence intervals will be reported for each time point. The distribution of titers will also be graphically summarized using reverse cumulative frequency distributions. Anatomical sites will be summarized separately.

Summaries of the ratio of serum to mucosal IgG concentration will be generated at each time point. Geometric means and confidence intervals will be reported and scatter plots of serum vs. mucosal IgG concentrations will be generated. Summaries of pairwise concentration ratios, comparing anatomical sites, will also be generated at each time point. Summaries will include geometric means and confidence intervals as well as graphical summaries.

All geometric mean calculations will use \log_{10} transformed data, and the anti-log of the resulting point estimates will be reported for means and confidence intervals. Missing immunogenicity data will not be imputed and no search for outliers will be performed. The logarithmic transformation is used to improve the distributional properties of the immunogenicity data to reduce the impact of potential outliers.

Additional supplementary and/or sensitivity analyses of the primary and secondary outcomes as well as analysis of the exploratory immunogenicity outcomes will be described in the separate SAP.

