2.1. Purpose of the Analyses

These analyses will assess the immunogenicity and safety of the multicomponent meningococcal serogroup B vaccine (4CMenB or Bexsero) against GC in comparison with a placebo vaccine (normal saline) and will be included in the clinical study report.

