3. STUDY OBJECTIVES AND ENDPOINTS

3.1. Study Objectives

3.1.1. Primary Objective

- To characterize the rectal mucosal IgG antibody response to GC elicited by the 4CMenB vaccine as compared with the placebo vaccine (normal saline) in healthy adult participants.

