3.3.2. Immunogenicity Outcomes

In the primary, secondary, and exploratory outcomes, the GMT for Enzyme-Linked Immunosorbent Assay (ELISA) will be calculated for Days 1, 29, 43, 57 and 181 for each treatment arm. The GMT is defined as:

$$GMT = \sqrt[n]{X_1 * X_2 * X_3 * \dots * X_n}$$

In practice, it is the equivalent of: $GMT = \text{Exp}\{[\log(X_1) + \log(X_2) + \dots + \log(X_n)] / n\}$

Where the X_1, X_2, \dots, X_n are the titers for each participant at a certain timepoint. A sample SAS code for calculating the geometric mean and the 95% confidence interval is shown below.

```
proc surveymeans  
  data=data geomean;  
  var variable;  
  run;
```

The geometric mean fold rise (GMFR) for ELISA titers will be calculated for Days 29, 43, 57, and 181 compared to baseline titer in each study arm. The fold change for each participant at each timepoint is calculated first by dividing the follow-up titer by the baseline titer, then the geometric mean and 95% confidence interval will be calculated for each treatment arm at each timepoint.

Similarly, the ratio of serum to mucosal (rectal, vaginal, and oropharyngeal) IgG will be calculated at each time point. The geometric mean and confidence interval will be calculated as above.

Percent inhibition of gonococcal adhesion to human cervical cell line by mucosal antibody is defined as:

$$100\% * [(Titer \text{ without mucosal antibody} - Titer \text{ with mucosal antibody}) / Titer \text{ without mucosal antibody}]$$

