4.2. Discussion of Study Design, Including the Choice of Control Groups

This study follows a double-blind, randomized, placebo concurrent control design. Participants receive either the multicomponent meningococcal serogroup B vaccine (4CMenB or Bexsero) against GC or saline placebo as their first study vaccination. After approximately 1 month, all participants will receive the second dose of study vaccine (or placebo). To date, there are no vaccines that are licensed in preventing gonorrhea, thus a placebo will be used as the comparator, which allows us to determine if the observed effects are due to the study product or other reason.

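### The primary and first secondary objectives compare 4CMenB with placebo, but no between-arm GMT ratio with a confidence interval is planned

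*SAP*

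**What the plan says.** The comparative intent is explicit. SAP 3.1.1 sets out to characterise the response "elicited by the 4CMenB vaccine as compared with the placebo vaccine (normal saline) in healthy adult participants", and SAP 3.1.2 words the serum IgG objective the same way. SAP 2.1 says the analyses assess immunogenicity and safety "against GC in comparison with a placebo vaccine (normal saline) and will be included in the clinical study report". SAP 4.2 justifies the placebo arm as the element "which allows us to determine if the observed effects are due to the study product or other reason".

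The planned analyses are all within arm:

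- Protocol 10.5.3: GMT and fold rise for "ELISA titers will be calculated for Days 1, 29, 43, 57, and 181 in each study arm".
- SAP 3.3.2, on fold rise: each participant's ratio to baseline is formed, "then the geometric mean and 95% confidence interval will be calculated for each treatment arm at each timepoint".
- SAP 8: "Immune responses for the study vaccine (4CMenB or placebo) will be summarized at each time point presented by study arm".
- SAP 8.1, 8.2 and the shells of Tables 14 to 17: N, GMT (95% CI) and GMFR (95% CI) in separate 4CMenB and placebo columns.
- SAP Tables 22 to 25: these do contain geometric mean ratios, but of serum to mucosa or of one site to another, within an arm.
- SAP 10 (Other Analyses) is marked not applicable.

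On testing, SAP 6.7 states: "No formal hypothesis test of the primary outcome will be performed". Protocol 10.1 permits between-group p-values but names no method, time point or estimate. A between-arm GMT ratio with a CI appears only in protocol 10.2, Table 2, as an illustration of precision. SAP 5 does not carry it over.

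**The concern.** The comparison named in the primary objective has no planned estimate. A fold rise within the vaccine arm compares vaccinees with their own baseline, not with placebo, so it does not serve the purpose that SAP 4.2 gives for having controls. Two one-sample intervals side by side do not give the size of the difference or its uncertainty.

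The absence of a formal test does not explain this, because a ratio with a CI is estimation. The gap begins in protocol 10.5.3 and the SAP repeats it. Baseline titre enters only through the per-arm fold rise, and sex only through descriptive Tables 15 and 17. Neither these nor the biopsy cohort adjusts a contrast, since there is none to adjust.

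If someone derives the ratio after the results are known, the variance method and the covariates become choices made with the data in view. With about 10 controls and 4:1 allocation, those choices change the interval materially.

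**Working it through.** **Inputs.** Protocol Table 2, gonococcal (Ng) OMV at 40/10: vaccine GMT 42224 (36161 to 49303), placebo GMT 34297 (20947 to 56156), printed ratio 1.23 (0.85 to 1.79). Strata come from Table 1 of either document; the planned placebo cells are 2, 2, 3 and 3.

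**1. Recover the SDs (ln scale).** s = [ln(U/L)/2] / t(0.975, n−1) × √n.

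- Vaccine: 0.310/2 = 0.155; 0.155/2.023 × √40 = 0.485.
- Placebo: 0.986/2 = 0.493; 0.493/2.262 × √10 = 0.689.

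**2. Reproduce Table 2.** The pooled variance is (39 × 0.485² + 9 × 0.689²)/48, so s = 0.529. The SE is 0.529 × √(1/40 + 1/10) = 0.187. The half-width is 2.011 × 0.187 = 0.376, a factor of 1.46. The ratio is 42224/34297 = 1.231, with CI 0.85 to 1.79 as printed. The same pooled t interval reproduces all 12 ratio CIs in the table.

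**3. Allow unequal variances (Welch).** Var = 0.485²/40 + 0.689²/10 = 0.0059 + 0.0475 = 0.0534, so the SE is 0.231 on 11.3 df. The interval spans a factor of 1.66 each side. The placebo arm supplies 0.0475/0.0534 = 89% of the variance.

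| Evaluable (vaccine/placebo) | Pooled (as printed) | Welch |
|---|---|---|
| 40/10 | 0.85–1.79 | 0.74–2.04 (11.3 df) |
| 35/8 | 0.81–1.87 | 0.69–2.21 |
| 30/6 | 0.77–1.97 | 0.60–2.53 (6.0 df) |

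**4. Coverage of nominal 95% intervals.** Simulation, 200,000 trials, true SDs 0.485 and 0.689, no covariates:

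| | Pooled | Welch |
|---|---|---|
| 40/10 | 0.890 | 0.948 |
| 30/6 | 0.882 | 0.946 |

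**5. Separate arm intervals against the ratio.** For N. meningitidis (Nm) whole cell at 30/6, the vaccine row of Table 2 reads "388023 | 262806, 572900 | 4.00 | 1.53, 10.47" and the placebo CI is 29287 to 321311. The arm intervals overlap, yet the ratio interval excludes 1. It still does under Welch: with SDs 1.043 and 1.141 and 6.8 df, the CI is 1.21 to 13.26.

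**6. A baseline-adjusted model.** Log titre on arm, Day 1 log titre, sex and biopsy cohort, Table 1 strata, 12,000 trials per setting. The documents give no baseline-to-post correlation, so a range is assumed. SEs at 40/10:

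| Assumed correlation | Post only | Change score | Adjusted | Adjusted vs post only | Adjusted vs change |
|---|---|---|---|---|---|
| 0.3 | 0.232 | 0.282 | 0.223 | −3 to −4% | −21% |
| 0.5 | 0.233 | 0.239 | 0.204 | −12% | −15% |
| 0.7 | 0.233 | 0.187 | 0.172 | −26% | −8% |

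At zero correlation, adjustment costs about 0.7% against post only. For this adjusted model with the unequal SDs, pooled-variance intervals cover 0.885 to 0.890 at 40/10 and 0.874 to 0.882 at 30/6. HC3 robust standard errors on residual df (45 at 40/10) give 0.948 to 0.950 and 0.939 to 0.940. With both SDs set to 0.689, pooled coverage is 0.946 to 0.952 and HC3 coverage 0.950 to 0.956.

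**The case against.** The strongest reply is that the analysis matches the endpoints, which are defined as GMTs per group, in a study that repeatedly calls itself descriptive and whose control arm was not sized on statistical criteria. Arm columns side by side, GMT plots with CIs and reverse cumulative curves do present both arms. This correctly limits the point: no test is missing. It does not supply an estimate for an objective worded as a comparison.

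Three narrower objections are right as far as they go.

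- The overlap example concerns a meningococcal control antigen, and it is the only one of Table 2's 12 blocks where arm overlap and the ratio interval disagree. For Ng OMV they agree at every sample size. The example shows that the two readings can differ, not that they would for the primary antigen.
- Listings 6, 9 and 10 give sex and participant-level titres by arm and visit, so a baseline-adjusted ratio could be rebuilt from listings, though not from the tables. What is lost is pre-specification.
- Table 2 hints at a pooled interval as the default. No analysis section adopts it, and with Table 2's own Ng OMV SDs it undercovers.

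The coverage figures are conditional on those SDs; with equal SDs the pooled interval is adequate. HC3 and the covariates are one reasonable choice. An unadjusted two-sample ratio with a stated CI method would also close the gap, less precisely if baseline predicts response.

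**Conclusion.** The concern holds on the text alone: no section of the protocol or SAP plans a between-arm GMT ratio with a CI for the primary or first secondary outcome, although the objectives and the rationale for the placebo arm call for that comparison. It should be corrected, and the correction is compatible with not testing a hypothesis.

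The size of what is left open is illustrative. On Table 2's Ng OMV figures at 40/10, moving from pooled to Welch widens the interval from a factor of 1.46 each side to 1.66, and the pooled interval's coverage is about 89% (88% at 30/6). These figures assume that serum SDs apply to rectal IgG and that the arms' SDs really differ. The gains from adjustment rest on an assumed correlation of 0.3 to 0.7. None of these assumptions bears on whether the estimate is missing.

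**What to change.** In SAP 8.1 and 8.2 and Tables 14 and 16, add the 4CMenB/placebo GMT ratio with 95% CI for each gonococcal OMV antigen (Ng 1291 and CNG20) at Days 29, 43, 57 and 181.

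- **Model:** log10 titre on arm, Day 1 log10 titre, sex and biopsy cohort, back-transformed. Use main effects only, given placebo cells of 2 to 3.
- **Variance:** name the method in advance, for example HC3 standard errors with residual df.
- **Zeros:** say how the rule in SAP 6.1 that only non-zero values enter geometric means applies to the model.
- **Status:** label the ratios as estimation without a formal test and without multiplicity adjustment, in line with SAP 6.7. Keep the by-arm GMT and GMFR rows.
- **Protocol:** add a matching sentence to 10.5.3 if it is amended.

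**Cost:** SAP wording, one model specification and, because the tables have a column per antigen, two added columns in each of Tables 14 and 16. That is 2 antigens × 4 days × 2 specimens = 16 fits, or 32 over both analysis populations. No new data are needed, and the covariates use three more model df.

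The real price is width, because the placebo arm governs the precision. At 40/10 the median HC3-adjusted interval spans a factor of 1.59, 1.53 or 1.43 each side at correlation 0.3, 0.5 or 0.7, against 1.66 for unadjusted Welch and 1.46 for unadjusted pooled. At 30/6, HC3 coverage is about 94%.
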